1.0 Objectives

1.1 Using cancer caregivers (CCGs) as a representative population of the larger CG population, our long-term goal is to conduct a large-scale fully powered trial evaluating a widely accessible and previously studied Qigong regimen (Eight Brocades, *Baduanjin Qigong*). The goal of this R34 is to conduct a mixed-methods pilot randomized controlled trial (RCT) to inform the feasibility and design of a future larger definitive trial.

Primary Objectives:

1. To finalize intervention content and delivery of both in-person community-based group and individual internet-based Qigong protocols.
2. To assess the 'learnability' of Qigong delivered in community-based group classes and via an internet-based protocol using a novel proficiency instrument.
3. To evaluate the feasibility of recruiting and retaining cancer caregivers into a 12-week clinical trial, and completing all outcomes testing protocols.

1.2 We hypothesize that participant recruitment, retention, and adherence to intervention and assessment protocols will comply with target goals. Feasibility will be assessed with respect to participant recruitment, retention, intervention adherence, and intervention acceptability. We will assess recruitment feasibility by the number of screened and eligible participants and the number refusing to participate. We will document reasons for refusal. This domain of feasibility will require: a) $\geq 50\%$ screened individuals are study eligible and b) $\geq 5-10\%$ of eligible participants are willing to consent. With a goal of $n = 54$ enrolled over a one-year period, we will need to screen 14 participants per month. Participant retention will be deemed feasible if loss to follow-up is $\leq 20\%$. Intervention adherence will require: a) $\geq 70\%$ participation in community or internet-guided classes and $> 50\%$ compliance with home practice guidelines. Qualitative interviews with CCGs, including those who drop out and have low adherence, will be used to further inform overall study feasibility, and facilitators and barriers to participation.

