5.0 Number of Subjects

LOCAL:

5.1 We expect to consent, enroll, and randomize a total of 54 CCGs.

5.2 The sample size was based on practical/budgetary constraints as well as a preliminary power analysis. A power analysis was conducted to determine the minimum sample

FULL PROTOCOL TITLE: CARING FOR CAREGIVERS WITH MIND-BODY EXERCISE

size that is required to find significance with a power set of .80, an alpha level at .05, correlation among the repeated measures of 0.3, and a moderate effect size of .25 using G*Power version 3.1. Based on the primary analysis, to ensure sufficient power on the repeated measure ANOVA (3 time points x 3 groups), a total of 48 participants are required. In consideration of 10-15% of attrition rate, a total of 54 participants will be recruited.

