6.0 Recruitment Methods

LOCAL:

- 6.4 Interested individuals identified through recruitment strategies will be provided contact information to call the study coordinator for an initial phone screen. The coordinator will use a phone screen script to review details of the study with potential participants. To conduct the initial screen, the coordinator asks participants a series of questions related to study inclusion criteria. If the participant meets the inclusion criteria the coordinator will continue the screen with questions about exclusion criteria. If the individual is eligible and interested, they will then be scheduled for an in-person visit to University of Houston, College of Nursing, to complete their baseline visit and receive their group assignment. At this visit, eligibility will again be confirmed by asking the same series of questions about inclusion and exclusion criteria to confirm their eligibility status. After we confirm eligibility, consent is obtained, and baseline assessments made. We will document reasons for refusal.
- 6.5 Multiple recruitment sites and methods will be used for recruitment. Our primary recruitment site will be MD Anderson Cancer Center (MDACC) facilitated by [name] (study consultant). The distribution of how subjects were contacted and participation rate will be systematically tracked using screening logs. Recruitment feasibility will be assessed by the number of screened and eligible participants and the number of CCGs refusing to participate. Participants may also be sourced from churches, other support groups, social media postings, or by word-of-mouth. Recruitment strategies include presenting the study at monthly staff meetings in various cancer subspecialties, providing study brochures to oncologists, nurses, and administrative staff to be passed on to patients and their families, presenting at CG support group events, and posting the study on relevant hospital web sites including those specific to recruiting volunteers into clinical trials. In addition, participants will be recruited through non-hospital online websites such as the Houston Chapter of the Oncology Nursing Society and the Family Caregiver Support Network. Other strategies include targeted advertising in local newspapers and posting of flyers in public places (e.g., library, senior centers).

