7.0 Study Timelines

7.1 For Cohorts 1 and 2, we will randomize (1:1:1) 24 CCGs to one of three conditions: (1) A community- based Qigong program; (2) an internet-based Qigong program; or (3) a self-care control group. For Cohort 3, we will randomize (2:1) 15 CCGs to one of two conditions: (1) an internet-based Qigong Program, or (2) a self-care control group. For Cohort 4, we will randomize (2:1) 15 CCGs to one of two conditions: (1) a community-based Qigong program, or (2) a self-care control group. Our primary outcomes are feasibility and acceptability.

7.2 Participants in the community-based programs will attend one, 75 minutes class per week supplemented by home practice (guided by printed materials) for 20 minutes on 3 additional days. Participants in the internet-guided program will be asked to follow two online sessions for 40 minutes each, also supplemented by home practice for 20 minutes on 3 additional days. Participants in both Qigong groups will commence training within 2 weeks of baseline visits. Caregivers randomized to either Qigong intervention can expect a total time commitment of 30 hours to complete all study related activities.

Individuals randomized to the self-care control group will be provided with an educational book on caregiving, they will also be provided with a “Self-Care Manual” that includes self-guided activities related to caregiving and caregiver health. Caregivers randomized to this group can expect about a 5-hour total time commitment to study related activities.

7.3 Baseline and 12-week assessments including psychosocial measures and QOL, physical function and cognitive measures will occur in person for all participants at the University of Houston College of Nursing in Sugarland, [name]. In addition, a short qualitative interview will be conducted with participants in the community-based and internet-based classes. A longer-term 6-month follow-up will assess psychosocial and QOL measures using a mail-in questionnaire packet. Primary analyses should be complete by 08/31/2021.

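### The consent condition for recruitment feasibility in section 1.2 (at least 5–10% of eligibles) is not a single threshold, and either bound is far below the 32–64% consent implied by screening 14 a month

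*Combined protocol and SAP*

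**What the plan says.** Section 1.2 (Objectives) of the combined protocol and SAP hypothesises that "participant recruitment, retention, and adherence to intervention and assessment protocols will comply with target goals". It then lists two requirements for recruitment feasibility: at least 50% of screened individuals are eligible, and at least 5–10% "of eligible participants are willing to consent". The next sentence gives the accrual plan: "With a goal of $n = 54$ enrolled over a one-year period", "we will need to screen 14 participants per month".

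Other sections bear on the point:

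- Section 5.1: "We expect to consent, enroll, and randomize a total of 54 CCGs".
- Section 6.4: "Interested individuals identified through recruitment strategies will be provided contact information to call the study coordinator for an initial phone screen". Eligibility is checked on that call and again at the baseline visit.
- Section 6.5: "Recruitment feasibility will be assessed by the number of screened and eligible participants and the number of CCGs refusing to participate". No cut-off is attached.
- Section 7.1: "Our primary outcomes are feasibility and acceptability".
- Section 19.1 describes recruitment with descriptive statistics and sets numerical success criteria for retention, attendance and practice compliance, but none for consent.

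**The concern.** Two things look wrong in adjacent sentences. First, a greater-than-or-equal sign in front of a range does not define a pass mark. The other rules in the same paragraph (eligibility, loss to follow-up, class participation, home practice) each give one number. Second, the consent floor and the monthly screening figure appear to belong to different plans, because consent of 5–10% among eligibles cannot yield 54 enrolled from 14 screened a month.

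Recruiting is part of primary objective 3, feasibility is a primary outcome, and the pilot exists to inform a definitive trial. If the listed conditions can be met while enrolment is far short of 54, a report could cite either the passed ratios or the missed goal, and the text does not say which governs.

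**Working it through.** **Inputs.** Goal of 54 in 12 months, 14 screened per month, eligibility condition of at least 50%, and consent condition of at least 5–10% of eligibles (all section 1.2). The documents give no expected eligibility rate and no expected consent rate. Eligibility of 50% is the stated floor; 75% and 100% are taken to show the range.

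**1. Can 14 a month be reproduced from the stated floors?** Screening per month = 54 / (12 × eligibility × consent).

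| Eligibility | Consent 10% | Consent 5% |
|---|---|---|
| 50% | 54 / (12 × 0.50 × 0.10) = 90 | 54 / (12 × 0.50 × 0.05) = 180 |
| 100% | 54 / (12 × 1.00 × 0.10) = 45 | 54 / (12 × 1.00 × 0.05) = 90 |

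No. The nearest figure, 45, is 45/14 = 3.2 times the stated 14, and the furthest is 180/14 = 12.9 times.

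**2. What consent rate does 14 a month imply?** Screened in a year: 14 × 12 = 168. Implied consent = 54 / (168 × eligibility).

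| Eligibility | Eligible | Consent needed for 54 |
|---|---|---|
| 50% | 84 | 54/84 = 64.3% |
| 75% | 126 | 54/126 = 42.9% |
| 100% | 168 | 54/168 = 32.1% |

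**3. Where does the range give two verdicts?**

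- Of 84 eligible: 4/84 = 4.8% fails 5% and 5/84 = 6.0% passes. 8/84 = 9.5% fails 10% and 9/84 = 10.7% passes. Counts of 5 to 8 pass at one bound and fail at the other.
- Of 168 eligible: 8/168 = 4.8% fails 5% and 9/168 = 5.4% passes. 16/168 = 9.5% fails 10% and 17/168 = 10.1% passes. Counts of 9 to 16 are ambiguous.

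**4. How small can enrolment be and still pass?** At 168 screened, the minimum passing counts are 5 (5% bound) or 9 (10% bound) with 50% eligible, and 9 or 17 with 100% eligible. Against 54, the shortfall runs from 1 − 17/54 = 68.5% to 1 − 5/54 = 90.7%.

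**5. How readily does the stricter bound pass?** Take 84 eligible and a binomial count X of consenters. The 10% bound is met when X ≥ 9. The true consent rates below are assumptions.

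| True consent | Expected enrolled (84 × rate) | P(X ≥ 9) |
|---|---|---|
| 10% | 8.4 | 0.466 |
| 15% | 12.6 | 0.900 |
| 20% | 16.8 | 0.992 |
| 25% | 21.0 | 0.9997 |

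Under these rates the chance of reaching 54 of 84 is negligible (about 10⁻¹⁸ at 20%).

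**The case against.** The strongest reply is that a minimum acceptable rate and a planning rate are different quantities. A reader might infer from step 1 that 14 a month is an error. The documents do not support that. The floors need not be the source of 14, and under section 6.4 the people screened are interested individuals who call the coordinator themselves, so consent of 32–64% may be realistic. What stands is that the planning rates are unstated and the floors cannot be their basis.

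A reader might also infer that a pass with low enrolment is likely. That is not supported either. Step 5 is conditional on assumed consent rates. The ambiguity between 5% and 10% also matters only when consent is near that range: with 84 eligible, the count falls between 5 and 8 with probability 0.59 at a true rate of 7.5%, but only 0.8% at 20%.

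The 69–91% shortfall holds only at 168 screened. Fourteen a month is given as a need, not a cap, and more screening would raise enrolment at the same consent rate. The upper passing count of 17 further assumes that everyone screened is eligible.

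Missing 54 would not be hidden: sections 1.2 and 5.1 state the number, and section 6.5 tracks screening and refusals. A pilot may reasonably keep rate criteria apart from accrual, so making all 54 a condition is partly a design preference. Finally, 5–10% may have been meant for a wider pool of people approached. The text says eligible participants and quantifies no such pool, so this remains a possibility and is itself a reason to define the denominator.

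None of this supplies a single cut-off or says how a passed ratio and a missed goal are to be combined.

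**Conclusion.** The point holds as a defective decision rule for part of a primary objective, and it should be fixed. The consent condition gives no single verdict for observed consent from 5% to just under 10%. Both bounds are roughly 3 to 13 times below the consent rate implied by 14 screened a month (32.1% to 64.3%, for eligibility from 100% down to 50%). At the planned 168 screened, the listed conditions can be met with 5 to 17 consenters, depending on bound and eligibility, and so hardly test the goal of 54. If true consent were 15–25% with 84 eligible, the 10% bound would be met with probability 0.90 to over 0.999 while about 13 to 21 enrol.

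The ambiguity and the implied rates follow from the documents' own figures. The pass probabilities rest on assumed consent, 50% eligibility and screening fixed at 168. The conclusion is neither that 14 is wrong nor that a misleading pass is to be expected.

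**What to change.** In section 1.2:

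- **(a) One cut-off.** Replace the range with a single consent percentage and define its denominator: eligible at the phone screen, confirmed eligible at baseline, or a wider approached pool. The cut-off may sit below the planning rate.
- **(b) Planning rates.** State the eligibility and consent rates behind 14 a month, or restate the monthly figure as 54 / (12 × eligibility × consent).
- **(c) The goal of 54.** State how the recruitment verdict treats the case where the ratios pass but 54 in 12 months is missed. Reporting accrual against 54 alongside the ratios would do; all 54 need not be a mandatory gate.

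The cost is wording. Design, procedures and data collection are unchanged, because sections 6.4 and 6.5 already provide for screening logs and recorded refusals. If a wider approached pool is chosen as the denominator, its size must also be counted, and the documents quantify no such pool at present. The downside is a stricter criterion. The documents do not give accrual status, although section 7.3 expects primary analyses to be complete by 08/31/2021. If accrual has begun, the cut-off must be set without reference to the screening logs or be reported as post hoc.

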2.0 Background

2.1 Longer life expectancies and an aging population mean that an increasing number of adults are likely to develop multiple comorbidities and rely on informal CGs for support.¹ Informal CGs, typically family members or friends, are responsible for caring for individuals with a variety of burdensome conditions including advanced age, dementia, and cancer. The average number of hours spent caregiving is often greater than 21 per week.² In addition to providing psychological support, CGs are also commonly responsible for relatively complex medical procedures, despite limited or no formal training, as well as taxing physical support (e.g., weight transfers, increased household chores). Collectively, these responsibilities result in substantial and chronic stress, with negative psychological and physiological effects on CGs' health.³⁻⁵ Informal CCGs provide 70 to 80% of care for those with cancer

FULL PROTOCOL TITLE: CARING FOR CAREGIVERS WITH MIND-BODY EXERCISE

and are involved during the cancer care trajectory from diagnosis to death.^{6,7} The burden of caring for someone with cancer can be extremely high; 50% of CCGs report increased levels of stress and depression with 40% indicating that they need help managing their own emotional and physical stress.² CG burden has even been identified as an independent predictor of caregiver mortality with a 63% increased risk of death.⁸ Additionally, research indicates that decreased CG QOL directly impacts the QOL of care recipients.⁹⁻¹⁰ Moreover, the burden among CCGs often persists for years after patients' initial cancer diagnosis, with evidence of long-term detriments to health and QOL.¹¹⁻¹⁴ Therefore, there is a pressing need to develop effective and practical interventions to prevent and manage the psychological and physical stressors that reduce QOL in CGs.

2.2 Not applicable.

2.3 Mind-body practices that target both psychological and physical dimensions of distress offer a promising and pragmatic therapeutic strategy for addressing the needs of CGs.¹⁵⁻¹⁷ However, the evidence required to guide such an approach is still limited in multiple ways. First, while a growing body of research supports mind-body practices such as Tai Chi, Qigong, yoga and meditation for a range of symptoms in patients with chronic disease,¹⁸⁻²² few large scale studies have evaluated impact of these practices in CGs. Of the studies which have evaluated CGs (mostly yoga or MBSR), many have utilized interventions tailored to patient-CG dyads.^{21, 23-26} Although this approach has merit, it may limit targeting CGs psychological and physical needs. Additionally, while many MBSR and yoga studies show positive effects on mental health, most do not include physical function and disability measures. Lastly, more widespread access to mind-body interventions targeting CGs has been challenged by economic, geographic, and time barriers.²⁷ Common barriers to in-person group classes (e.g., issues with CG travel to community-based programs) might be overcome with internet-based delivery of intervention, offering an alternative for some CGs that may significantly increase access and adherence. While internet delivery of individual-based mind-body practices is increasingly studied and shows promise,¹ this approach has not been explored in CG populations.

Qigong is an increasingly popular multi-modal mind-body exercise that shows promise in addressing a broad range of psychosocial and physical factors highly relevant to CGs. Sharing many characteristics with Tai Chi, Qigong incorporates elements of slow gentle movement, breath training, and a number of cognitive skills including heightened body awareness, focused mental attention, and imagery—which collectively may afford greater benefits to health compared to unimodal therapies.²⁸⁻³⁰ In contrast with typical Tai Chi choreography, some Qigong regimens focus on simpler repetitive movement phrases, which make them easier to learn both through in-person instruction and especially via video-guided instruction. A robust evidence base supports that across adult populations, Qigong and Tai Chi training in groups can improve multiple domains of physical and emotional health, including those highly relevant to CGs such as depression,³¹⁻³³ anxiety,^{31, 33} poor sleep,³³⁻³⁶ musculoskeletal strength,^{34, 36} balance during functional activities,^{34, 36} pain,^{31, 37-40}

FULL PROTOCOL TITLE: CARING FOR CAREGIVERS WITH MIND-BODY EXERCISE

and core underlying physiological processes such as inflammation.^{41, 42} Reduction of overall distress and improved long-term prognosis is also supported by improvements in broader constructs including overall QOL^{31, 33} and self-efficacy.^{15, 34, 43} While Qigong is increasingly being used to help manage health and distress in CGs, (including at leading academic medical centers like MD Anderson Cancer Center and Harvard's Dana-Farber Cancer Institute), we are not aware of any studies to date evaluating Qigong for CGs.

3.0 Inclusion and Exclusion Criteria

3.1 Inclusion criteria include (1) age ≥ 35 years; (2) a spouse, partner, family member, or friend providing physical, emotional, and/or financial support for a cancer patient; (3) able to understand, speak, and read English; (4) minimum level of 3 on the National Comprehensive Cancer Network's (NCCN) Distress Thermometer adapted for CGs; and (5) able to provide informed consent. Exclusion criteria include (1) unstable illness (e.g., recent hospitalization, unstable cardiovascular disease, active cancer); (2) psychiatric disorders (e.g., unmanaged depression or psychosis, substance abuse, severe personality disorder); (3) degenerative neuromuscular condition (e.g., Parkinson's disease, multiple sclerosis); (4) inability to walk continuously for 15 minutes; (5) recent history of attending regular Qigong or similar (e.g., yoga or Tai Chi) classes defined as 20 or more classes in the past 6 months; or (6) participation in more than 240 minutes of moderate-intensity exercise per week (as these individuals already exhibit high exercise self-efficacy and are less likely to be otherwise symptomatic).

3.2 Potential subjects will be screened for eligibility based on these criteria over the phone. This call will be based on a script that comprehensively addresses all inclusion and exclusion criteria to ensure that each potential participant is appropriately screened.

3.3 This study will not include adults unable to consent, individuals who are not yet adults (infants, children, teenagers), pregnant women, prisoners, students for whom the researchers have direct access to/influence over grades, or economically and/or educationally disadvantaged persons.

4.0 Vulnerable Populations

4.1 Not applicable.

5.0 Number of Subjects

LOCAL:

5.1 We expect to consent, enroll, and randomize a total of 54 CCGs.

5.2 The sample size was based on practical/budgetary constraints as well as a preliminary power analysis. A power analysis was conducted to determine the minimum sample

FULL PROTOCOL TITLE: CARING FOR CAREGIVERS WITH MIND-BODY EXERCISE

size that is required to find significance with a power set of .80, an alpha level at .05, correlation among the repeated measures of 0.3, and a moderate effect size of .25 using G*Power version 3.1. Based on the primary analysis, to ensure sufficient power on the repeated measure ANOVA (3 time points x 3 groups), a total of 48 participants are required. In consideration of 10-15% of attrition rate, a total of 54 participants will be recruited.

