9.3 The Qigong Instrument used is the Eight Brocade Protocol. Qigong is an increasingly popular multi-modal mind-body exercise that shows promise in addressing a broad range of psychosocial and physical factors highly relevant to CGs. Sharing many characteristics with Tai Chi, Qigong incorporates elements of slow gentle movement, breath training, and a number of cognitive skills including heightened body awareness, focused mental attention, and imagery—which collectively may afford greater benefits to health compared to unimodal therapies.²⁸⁻³⁰

Week	Activities	Approx. Duration (in minutes)
1-2	Check-in	2
	Qigong Warm-up Exercises	
	Qigong Swinging and Drumming the Body	
	Swinging Up and Down	
	Spiraling the Waist	
	Mindful stretching	
	Lower Extremities (feet, ankles, knees)	20
	Upper Extremities (hands, arms, shoulders)	
	Spinal Cord Breathing	
	Washing with Qi from the Heaven	
Tan Tien Breathing		
Introduction to Eight Brocades Movements #1-4	35	
#1 Holding the Hands High to Regulate Internal Organs		
#2 Posing as an Archer Shooting Both Left- and Right-Handed		
#3 Holding One Arm Aloft to Regulate Spleen and Stomach		
#4 Looking Backwards to Prevent Sickness and Strain		
Cool-Down Exercises	3	
Self-massage and meridian tapping		
3-8	Check-in	2
	Qigong Warm-up Exercises	10
	Review/ Practice Eight Brocades Movements #1-4	15
	Learn and practice Eight Brocades Movements #5-8	30
	#1 Swinging the Head and Lowering the Body to Relieve Stress	
	#2 Moving Hands Down Back and Legs, and Touching Feet to Strengthen Kidneys	
	#3 Thrusting Fists and Making Eyes Glare to Enhance Strength	
	#4 Raising and Lowering the Heels to Cure Diseases	
Cool-Down Exercises	3	
9-12	Check-in	2
	Qigong Warm-up Exercises	10
	Review/ Practice/ Refine Eight Brocades Movements #1-8	45
	Cool-Down Exercises	3

9.4 In addition to caregiver distress, medical history and demographics, the following outcomes will be assessed at baseline, 12-weeks, and 6-months:

The following will be measured at baseline and 12-weeks:

FULL PROTOCOL TITLE: CARING FOR CAREGIVERS WITH MIND-BODY EXERCISE

- Grip strength of the dominant hand will be measured using a **Jamar hydraulic hand dynamometer** (Patterson Medical – Canada, Mississauga, ON, CAN).⁴⁴

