Estimating variance for future power calculations. We will use linear mixed models with fixed effects of visit and treatment x post-baseline visit interaction and unstructured covariance among repeated measures to analyze efficacy outcomes. This will yield six variance components required for future power calculations. The Wald statistic from the treatment x visit interaction testing 12-week treatment-dependent response will be used to estimate the effect of Qigong and as a criterion for selecting outcomes that are potentially sensitive to Qigong. Selection of the outcomes to include in our future trial, and which to select as the primary outcome, will also be

FULL PROTOCOL TITLE: CARING FOR CAREGIVERS WITH MIND-BODY EXERCISE

guided by consideration of clinical relevance, participant burden, and cost. The study will have 80% power to identify the outcome that is truly most responsive to Qigong from among the 14 measures calculated from the 12 assessments completed at 12 weeks if the most responsive measure is associated with an effect size at least 0.43 SD greater than the others.

Inter-rater reliability and validity testing of proficiency instrument. Inter-rater reliability will be evaluated using Cohen's Kappa statistic. Validity testing based on cross-sectional comparisons of proficiency scores and practitioner's years of training will utilize Pearson's correlations. Associations between longitudinal changes in proficiency and clinical outcomes will be evaluated using mixed model approaches described above.

Qualitative analysis. Semi-structured qualitative interviews will be audio recorded and transcribed verbatim. Thematic analysis will be informed by grounded theory methods to guide description of qualitative interviews. Questions will focus on facilitators/barriers to recruitment/participation, and acceptability of the intervention and its specific components. Two investigators will independently code transcripts to identify emergent themes in an iterative process until thematic saturation is reached as in prior studies.^{47, 48 49-51} Transcription, coding, and analysis will be conducted in NVivo v11.

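### The 80% power in section 5.2 belongs to a repeated-measures ANOVA that the plan does not run; power for the planned 12-week test is not stated

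*Combined protocol and SAP*

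**What the plan says.** Section 5.2 gives two grounds for the sample size: practical and budget limits, and a preliminary power calculation. The calculation seeks the minimum sample "size that is required to find significance with a power set of .80", with "an alpha level at .05", "correlation among the repeated measures of 0.3" and "a moderate effect size of .25 using G*Power version 3.1". It concludes that, for what it calls the primary analysis, "to ensure sufficient power on the repeated measure ANOVA (3 time points x 3 groups), a total of 48 participants are required". Allowing for 10–15% attrition, the target becomes 54.

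Other sections describe something different:

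- Section 7.1: "Our primary outcomes are feasibility and acceptability".
- Section 19.1, in the paragraph on estimating variance, fits linear mixed models with an unstructured covariance to the efficacy outcomes. The test it names is "The Wald statistic from the treatment x visit interaction testing 12-week treatment-dependent response". It is used to estimate the Qigong effect and to help choose outcomes for the later trial.
- Section 9.4 introduces grip strength, Timed Up-and-Go, Digit Span and Trail Making with "The following will be measured at baseline and 12-weeks". Section 7.3 limits the 6-month mailing to psychosocial and quality-of-life measures.

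**The concern.** The only sample-size power figure is tied to an analysis that appears nowhere in section 19.1 and that section 7.1 does not treat as primary. It also assumes three visits, which the physical and cognitive measures do not have.

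The consequence is mainly one of interpretation. Section 19.1 uses the 12-week statistic as one criterion for selecting outcomes for the definitive trial. A team relying on the 80% in 5.2 could read an unremarkable 12-week result as evidence that an outcome does not respond to Qigong, when the chance of detecting a response was never worked out.

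**Working it through.** **Inputs.** From 5.2: f = 0.25 (read as Cohen's f, the G*Power ANOVA metric), ρ = 0.3, α = 0.05, 3 groups, 3 times. From 7.1: 24 at 1:1:1 (8/8/8), 15 at 2:1 (10 internet, 5 control) and 15 at 2:1 (10 community, 5 control), which gives 18/18/18. From 1.2: loss to follow-up of up to 20% is tolerated, and 54 × 0.8 ≈ 43 completers.

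**1. Reproducing the 48.** For the group × time interaction with sphericity, λ = f²Nm/(1 − ρ), df1 = (g − 1)(m − 1), df2 = (N − g)(m − 1). With N = 48, m = 3, g = 3: λ = 0.0625 × 48 × 3/0.7 = 12.86, df = 4 and 90, power 0.81. N = 47 just misses 0.80, so 48 is confirmed. The within-subject main effect would need 38 and the between-group effect 86, so the 4-df interaction is what was powered.

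**2. Same formula, two visits.**

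| Completers | λ | df | Power |
|---|---|---|---|
| 48 | 0.0625 × 48 × 2/0.7 = 8.57 | 2, 45 | 0.72 |
| 43 | 7.68 | 2, 40 | 0.66 |
| 58 | 10.36 | 2, 55 | 0.81 |

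Reaching 0.80 takes 58 completers (60 for equal arms). This two-visit ANOVA is not planned either. It shows only that the figure in 5.2 depends on the third visit.

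**3. What f = 0.25 implies at 12 weeks.** The documents give no mean pattern. Take SD 1 and two equally effective Qigong arms, so the group pattern is (0, 1, 1), with mean squared deviation 2/9.

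- Effect fully present at 12 weeks and held, time pattern (0, 1, 1): interaction root mean square √(2/9 × 2/9) = 0.2222. Scale 0.25/0.2222 = 1.125, so the 12-week difference is about 1.13 SD.
- Effect linear over the three visits, (0, 0.5, 1): √(2/9 × 1/6) = 0.1925. Scale 0.25/0.1925 = 1.299, half of which is present at 12 weeks: 0.65 SD.

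**4. Power of the 12-week contrast, one Qigong arm v control.** Approximating the mixed model by a baseline-adjusted comparison, SE = √[(1 − ρ²)(1/n₁ + 1/n₂)] = √(0.91 × 2/18) = 0.318. Two-sided α = 0.05 is assumed, because 19.1 states none.

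| 12-week difference | Difference/SE | Power |
|---|---|---|
| 0.5 SD (assumed) | 1.57 | 0.33 |
| 0.65 SD | 2.04 | 0.51 |
| 1.13 SD | 3.54 | 0.93 |

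A 2-df comparison of all three arms gives 0.52 and 0.95 for the last two rows.

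**5. Difference detectable with 80% power.**

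| Setting | One arm v control | Qigong arms pooled v control |
|---|---|---|
| ρ = 0.3, no loss | 0.92 SD | 0.79 SD |
| ρ = 0.3, 20% loss | 1.04 SD | 0.88 SD |

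At ρ = 0.7 with no loss, the one-arm figure falls to about 0.69 SD.

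**6. Feasibility precision.** For 80% retention at n = 54: 1.96 × √(0.8 × 0.2/54) = 0.107, or about ±10.7 points.

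**The case against.** The strongest defence is that little depends on this figure. The trial is a feasibility pilot, 5.2 says openly that budget helped set the size, and 19.1 uses the 12-week statistic for estimation and outcome selection without setting an alpha. The mixed model is also not a wholly different design: its six variance components imply the same three visits for the psychosocial and quality-of-life outcomes. All of this stands and limits the consequence, but it does not put the ANOVA into the analysis plan.

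Section 19.1 also carries its own 80% figure. That figure is the chance of picking the most responsive of 14 measures when it leads the others by at least 0.43 SD. It concerns ranking and gives no power to detect an effect.

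A reader might go further and infer that the 12-week test lacks 80% power, or has less than half of it. The documents do not support that. They state no 12-week effect, and 0.5 SD is an outside assumption. The plan's own f = 0.25 gives 0.93 if the effect is fully present at 12 weeks. At 0.5 SD, pooling the Qigong arms (36 v 18) gives 0.43, and ρ = 0.7 gives 0.53 for one arm. Equally, 0.93 is no reassurance: it needs each Qigong arm to be about 1.13 SD better than control, which a reader would not gather from an effect labelled moderate.

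**Conclusion.** The point holds as a mismatch between the sample-size statement and the analysis plan. The 80% in 5.2 is arithmetically correct for a three-visit, three-group interaction test, but the plan does not perform that test and cannot do so for the two-visit measures. Power for the planned 12-week test is unstated and cannot be taken from 5.2. Across the effects considered it runs from about 0.33 to 0.93 for one arm against control.

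Those figures assume ρ = 0.3, SD 1, 18 per arm with no loss, equally effective Qigong arms when f is converted, no cohort effects, and a baseline-adjusted approximation to the mixed model. Section 19.1 does not say whether the contrast is per arm, pooled or 2-df. The statement should be corrected; the design need not change.

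**What to change.** In section 5.2:

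- Remove the statements that the repeated-measures ANOVA is the primary analysis and that 48 participants give it 80% power.
- State that 54 rests on budget and on feasibility precision (80% retention estimated to about ±10.7 points), in line with the primary outcomes in 7.1.
- Report the 80% detectable 12-week difference from step 5 with its correlation, loss and choice of contrast, and say that it shrinks if the correlation is higher.

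Add a sentence to 19.1 saying that its 80% figure concerns ranking the 14 measures, not detecting an effect. The cost is some rewording and a less favourable stated figure. No extra participants or assessments are needed.
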